## 1 PROTOCOL SUMMARY

### 1.1 SYNOPSIS

**Title:** Piloting ‘mPal,’ a Multilevel Implementation Strategy to Integrate non-hospice Palliative Care into Advanced Stage Lung Cancer Treatment

**Study Description and Objectives:**

This is a pilot RCT (40 patients mPal; 40 patients usual care; 6 providers not randomized) to test the feasibility and acceptability of a multilevel implementation strategy for outpatient palliative care (PC).

#### Primary Objectives

1. Evaluate mPal’s feasibility and acceptability. We hypothesize we will be able to enroll  $\geq 60\%$  of asLC patients we approach (primary feasibility outcome), retain  $\geq 60\%$  for one-month follow-up, and achieve mean patient and provider feasibility ratings of  $\geq 3.5/5$ . For acceptability, we hypothesize we will be able to achieve mean patient and provider acceptability ratings of  $\geq 3.5/5$ . We anticipate qualitative data (n = 40 mPal patient interviews; n = 6 provider interviews) will further support the ease of use and clinical value of mPal.
2. Obtain preliminary data on effectiveness and equity outcomes for a planned trial. In line with best practices for pilot studies, we are not testing formal hypotheses for effectiveness outcomes; however, we will measure patient and provider PC knowledge and motivation and PC referrals, which we expect will improve with mPal. For equity outcomes, we will explore whether mPal appears similarly effective for patients with different characteristics (e.g., rural vs. urban, health literacy, income, race) by analyzing survey and semi-structured intervention data from mPal patients (n = 40).

**Endpoint:**

Feasibility, primary endpoint defined as  $\geq 60\%$  eligible and approached patients enrolled

**Study Population:**

86 (n = 40, mPal; n = 40 usual care) patients with stage IIb-IV non-small cell lung cancer or extensive stage small cell lung cancer, at least 3 weeks into treatment, ECOG 0-3, English speaking.  
(n = 6) oncology providers who provide care at least a half day/week to advanced stage lung cancer patients.

**Stage:**

Stage I (Pilot –Feasibility testing)

[figure not shown]
**Facilities Enrolling:** UK Markey Cancer Center

**Description of Study Intervention:** Multilevel implementation strategy to educate patients and providers about palliative care, identify patient palliative care needs, and facilitate referrals during treatment. mPal patient content includes 1) educational video, 2) assessment of PC knowledge, 3) assessment of PC needs, and 4) assessment of whether patients would like to meet with PC/discuss PC with their provider. mPal's provider content includes an educational presentation.

**Study Duration:** 3 months (patient participation)

**Participant Duration:**  
Patients: ~2.5 hours over 6-10 weeks  
Providers: ~35-40 minutes over 12 weeks

## 1.2 SCHEMA

**Note.** T0 = baseline; T1 = assessment (~3-4 weeks after baseline); T2 = 8±3 week follow-up (after T0); T3 = ~3-month post-mpal implementation

## 2 INTRODUCTION

### 2.1 STUDY RATIONALE

Over 130,000 people are diagnosed with advanced stage lung cancer (asLC) in the U.S. each year. asLC patients experience significant psychological and physical sequelae from the disease and its treatment. Of the few supportive interventions tested in asLC patients, palliative care (PC) unequivocally has the strongest evidence base for addressing asLC patients' physical and psychological concerns. PC is an interdisciplinary approach to managing patients' physical, mental, and spiritual concerns. Multiple randomized controlled trials have shown delivering PC alongside cancer treatment improves asLC patient outcomes (e.g., symptom burden, quality of life) and reduces care costs. The evidence for PC is so strong that national clinical oncology guidelines now state PC should be delivered to all asLC patients within 12 weeks of starting cancer treatment. Despite these guidelines, less than 15% of asLC patients receive PC.

Underutilization of PC is an implementation problem.

Barriers to implementing PC at multiple levels are well documented. Most asLC patients 1) do not know what PC is or what concerns it can address, 2) mistakenly equate PC with end of life, and 3) are reluctant to seek PC services without their cancer provider's recommendation. Cancer care providers 1) do not understand how PC can help manage patient concerns during cancer treatment, 2) do not have time to adequately assess and discuss concerns that PC could manage, and 3) fear patient reactions when mentioning PC. Finally, healthcare systems rely on providers to refer patients to PC, but do not provide the tools or training needed to support PC communication and referrals.

Our preliminary work has identified a multilevel implementation strategy as a promising approach to improve utilization of PC. We have developed our multilevel implementation strategy, called mPal, with patient, provider, and system administrator feedback. We now propose to conduct a pilot study of the mPal intervention with 60 patients (30 intervention, 30 control). Patients will be randomized to mPal's patient-level implementation strategies or usual care; provider and system intervention components will not be randomized.

### 2.2 BACKGROUND

**A.1. Advanced stage lung cancer (asLC) is common, highly burdensome to patients, and disproportionately affects rural residents.** Lung cancer has the second highest cancer incidence and highest cancer mortality in the U.S. Each year, roughly 130,000 people are diagnosed with asLC. asLC is associated with high physical and psychosocial morbidities, including poorer physical and role function, higher depression, and more unmet supportive care needs compared to other cancers. asLC disproportionately affects rural, impoverished, medically underserved residents. Kentucky leads the nation in asLC incidence and mortality.

**A.2. Palliative care (PC) is an evidence-based approach that mitigates patient burden, but it is underutilized.** PC is an interdisciplinary approach to address the psychological, physical, and spiritual concerns of patients facing serious illness. In asLC, delivering palliative care alongside cancer treatment has improved patient symptom burden, quality of life, mental health, as well as key care quality outcomes such as shared decision-making and appropriate end-of-life care. The evidence behind PC is so strong that national guidelines and accrediting agencies now stipulate palliative care should be delivered to all asLC patients within 12 weeks of starting treatment.

**A.3. Overcoming barriers to PC implementation is a multilevel problem.** Unfortunately, factors at the patient, provider, and healthcare system level lead to underutilization of PC (Fig. 1). Less than 15% of patients who could benefit from PC utilize it. Most patients have poor PC knowledge (i.e., do not know what palliative care is or what concerns it can address, equate PC with end of life, and/or fear using it means stopping cancer treatment), will not seek PC without a provider recommending it, and under-report PC concerns to their oncology team (see Preliminary Data). Providers often also have poor PC knowledge (i.e., do not understand how PC can help manage patient concerns during treatment, equate it with end of life), are uncertain how to talk about PC with patients, and face time constraints during clinic visits to assess and address PC needs. Most healthcare systems rely on providers to refer patients to PC, yet do not have systems in place to help identify appropriate patients and facilitate referrals. Collectively, barriers to PC utilization fall into determinants of knowledge, motivation, and opportunity (Fig. 1).

[figure not shown]

Figure 1. Conceptual Model of PC Implementation Problem

**A.4. Existing interventions do not address multilevel determinants of PC.** A multilevel strategy to address the problem of underutilization of PC has not been tested. Multilevel interventions target two or more levels of patients, providers, or healthcare systems. In cancer care, these have been successfully developed and applied to improve cancer screening. They have not been developed and applied to PC implementation. Instead, interventions targeting individual barriers to PC utilization have been developed and tested. While showing some benefit, every intervention to date has significant shortcomings. Either they lack educational components to address knowledge barriers at the patient and provider levels, do not address provider motivation to use PC in clinical practice, or do not address system-level barriers to integrating PC. Critically, none have been designed for implementation in both community and academic cancer care settings—a major shortcoming given that most cancer care occurs in the community and that asLC disproportionately affects rural residents. A multilevel implementation strategy to address all key determinants of PC utilization is clearly needed.

### 3 OBJECTIVES

#### PRIMARY OBJECTIVES

1. **Evaluate mPal's feasibility and acceptability.** We hypothesize we will be able to enroll  $\geq 60\%$  of asLC patients we approach (primary feasibility outcome), retain  $\geq 60\%$  for one-month follow-up, and achieve mean patient and provider feasibility ratings of  $\geq 3.5/5$ . For acceptability, we hypothesize we will be able to achieve mean patient and provider acceptability ratings of  $\geq 3.5/5$ . We anticipate qualitative data ( $n = 30-40$  mPal patient interviews;  $n = 6$  provider interviews) will further support the ease of use and clinical value of mPal.
2. **Obtain preliminary data on effectiveness and equity outcomes for a planned trial.** In line with best practices for pilot studies, we are not testing formal hypotheses for effectiveness outcomes; however, we will measure patient and provider PC knowledge and motivation and PC referrals, which we expect will improve with mPal. For equity outcomes, we will explore whether mPal appears similarly effective for patients with different characteristics (e.g., rural vs. urban, health literacy, income, race) by analyzing survey and semi-structured intervention data from mPal patients ( $n = 30-40$ ).

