### 4 STUDY DESIGN

#### 4.1 OVERALL DESIGN

This is a Stage I, single-site trial to test the feasibility and acceptability of a novel intervention, mPal, through a pilot randomized controlled trial. Patient components are randomized. Provider components are not randomized. mPal is a multilevel implementation strategy designed to educate patients and providers about palliative care, identify patient palliative care needs, and facilitate referrals to palliative care during advanced stage lung cancer treatment.

To accomplish study objectives, we will conduct a pilot randomized controlled trial of the mPal protocol with 60 advanced stage lung cancer patients (40 mPal; 40 usual care); 6 oncology providers will be recruited and receive the provider components of mPal. The primary feasibility outcome that will be tested is patient enrollment ( $\geq 60\%$ ). We will also collect preliminary patient- and provider-reported data on effectiveness outcomes (e.g., PC knowledge), PC referrals (from the EHR), and will explore ways to improve effectiveness and equity outcomes (i.e., equitable reach of intervention) through semi-structured interviews with a purposive sample of mPal patients ( $n = 30-40$ ) and providers ( $n = 6$ ). See Study Schema for assessment timepoints.

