#### 4.2 SCIENTIFIC RATIONALE FOR STUDY DESIGN

In line with best practices for pilot studies, we are testing feasibility, not formal hypotheses surrounding effectiveness outcomes. We are not randomizing provider and system-level strategies because 1) we do not plan to randomize providers in our next trial (rather, clinics will be randomized to start mPal at different times through a stepped-wedge design); and 2) intervention contamination would occur within the clinic.

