**Table 2. Aim 1 and 2 Measures**

Construct	Description	Data Sources	Level		Schedule
			Pt	Pv/Sy	
Aim 1. Implementation Outcomes					
Feasibility	FIM  : 4 item implementation measure of intervention feasibility ( $\alpha = .89$ ); Individual interviews (pts, pvs)	Survey; interviews	X	X	mPal Patients: T1 Providers: T3
Acceptability	AIM  : 4 item implementation measure of intervention acceptability ( $\alpha = .85$ ) individual interviews (pts, pvs)	Survey; interviews	X	X	mPal Patients: T1 Providers: T3
Aim 2. Effectiveness and Equity Outcomes related to Planned Future Trial					
PC referral	Proportion of patients in each arm who receive a referral to PC within 1-month (survey) and 3-months (EHR) post-mPal intervention	EHR, Survey	X	X	Patients: T2 (survey); System: 3-months post intervention (EHR)
PC knowledge	HINTS PC  : 10 items; assesses self-reported PC knowledge and PC perceptions. PACKS	Survey	X	X	Patients: T0, T1 (mPal only), T2 Providers: T0, T1, T3
Motivation to use PC	PCAS-9  : 9 items; assesses emotional, cognitive, and behavioral components of motivation to use PC ( $\alpha$ 's = .70-.90)	Survey	X	X	Patients: T0, T1 (mPal only), T2 Providers: T0, T1, T3
Opportunities to use PC	5 items; perceived ability to access PC. Based on preliminary study and literature. 	Survey,	X	X	Patients: T0, T2 Providers: T0, T3
PC discussion	2 survey items; Interview questions to supplement (experiences discussing PC during clinical encounters, quality of discussion, how mPal was used)	Survey, depth interviews	X	X	Patients: T0, T2 Providers: T0, T3
Demographics	15 items; sociodemographics, health literacy  (pts), PC training (providers)	Survey	X	X	Patients: T0 Providers: T0
Equity	Characteristics of mPal patients who do/do not seek PC referral and do/do not show knowledge increase; Interview with those who do/do not use PC; barriers	Survey, interviews	X	X	mPal Patients: T2, 3m post intervention

Note. Pt = Patient; PV = provider; Sy = System; T = timepoint; T0 = baseline; T1 = post mPal app viewing or knowledge check (pt assessment); post webinar viewing (providers); T2 = 8-week follow-up (pt assessment); T3 = post-patient-level intervention period (for providers)

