#### 10.4.3 ANALYSIS OF THE SECONDARY ENDPOINT(S)

We will describe pre-post changes in the patient-reported outcome variables related to a future trial using univariate and bivariate statistics. Our chief goals will be to estimate the standard deviations of our key variables for use in planning future studies. We will examine, through the use of t-tests, whether pre-post changes in the mPal differ significantly from pre-post changes in the control group. If our intervention is successful, we would expect to see significantly greater improvement over time in our effectiveness outcomes (PC knowledge, motivation) in treatment vs. control. We will also examine correlations between changes in these measures and PC referrals; we expect changes in PC knowledge and motivation variables will be positively correlated with changes in PC referrals within both treatment and control groups.

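### Objective 2 asks whether mPal is similarly effective across patient groups but uses mPal patients only, which can show reach and response but not whether the effect differs

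*Combined protocol and SAP*

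**What the plan says.** Objective 2 appears in the Synopsis (Section 1.1) and in Section 3. Both state that "we will explore whether mPal appears similarly effective for patients with different characteristics", with rural or urban residence, health literacy, income and race as examples, "by analyzing survey and semi-structured intervention data from mPal patients". The number of mPal patients is 40 in the Synopsis and 30–40 in Section 3.

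The Equity row of Table 2 (Section 9.1) keeps the same restriction. Its measure is "Characteristics of mPal patients who do/do not seek PC referral and do/do not show knowledge increase", and only mPal patients are scheduled for it.

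Section 4.1 gives equity a different meaning: the study "will explore ways to improve effectiveness and equity outcomes (i.e., equitable reach of intervention) through semi-structured interviews".

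The outcomes concerned are measured in both arms. The Table 2 referral row is "Proportion of patients in each arm who receive a referral to PC". The patient schedule for knowledge is "Patients: T0, T1 (mPal only), T2", so only T1 is missing in usual care. Section 10.4.3 uses the control arm for the overall question, "whether pre-post changes in the mPal differ significantly from pre-post changes in the control group", but neither it nor Section 10.4.1 plans an arm comparison by patient characteristic. Section 4.2 adds that "we are testing feasibility, not formal hypotheses surrounding effectiveness outcomes".

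**The concern.** Whether an intervention is similarly effective in two groups is a question about two differences from usual care. Data from the mPal arm alone give one side of each difference. They can describe who is reached and who responds, which is the Section 4.1 meaning, but not whether the effect is alike.

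Measuring change from baseline does not repair this. A referral received during follow-up has no pre-intervention value to subtract. A change in knowledge includes whatever would have changed without the patient component, for example through repeat testing or through the provider education, which is not randomized and can reach both arms.

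The equity results are preliminary data for a planned trial. Read as effectiveness, the mPal-only tables could report a disparity where effects are equal, or none where they differ.

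**Working it through.** The plan gives no effect size, SD or precision for the equity question, so there is no figure of its own to reproduce. The 80 patients in Section 10.2 are justified by enrollment and retention. The inputs from the documents are 40 patients per arm (Section 10.3), the 60% retention target (Section 3) and an expected 9% Black or African American patients (Section 5.6). Referral rates, subgroup splits and correlations below are assumptions.

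**What the mPal-only contrast estimates.** Within each subgroup, the expected mPal outcome equals the usual-care outcome plus the effect. Subtracting subgroups:

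mPal-only gap = (difference in effect) + (difference under usual care).

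Only a control arm separates the two terms.

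**Referral.** Assume 20 rural and 20 urban patients per arm.

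| | Rural, mPal / usual care | Urban, mPal / usual care | Effect, rural | Effect, urban |
|---|---|---|---|---|
| Case 1 | 30% / 5% | 45% / 20% | +25 points | +25 points |
| Case 2 | 30% / 15% | 45% / 15% | +15 points | +30 points |

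The mPal columns are identical, so the mPal-only table has the same expected values in both cases. Exact binomial probabilities:

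- mPal-only, either case: urban higher 0.796, tie 0.080, rural higher 0.124.
- Both-arm contrast, case 1: favors urban 0.448, tie 0.109, favors rural 0.442.
- Both-arm contrast, case 2: favors urban 0.747, tie 0.077, favors rural 0.176.

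The both-arm contrast is centered on the right value in each case, but it is imprecise.

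**Knowledge.** A simulation with 20 patients per subgroup per arm, in SD units of change, shows both errors. With equal effects (0.5 in both subgroups) and usual-care change differing by 0.5, the mPal-only contrast averaged 0.496 and the both-arm contrast −0.002. With effects of 0.8 and 0.3 and an opposite 0.5 difference under usual care, the averages were 0.001 and 0.502.

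**Precision of the both-arm contrast.** For referral, the 95% half-width is 1.96 × √(Σ p(1−p)/n):

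- Case 1, 20 per cell: 1.96 × √((0.21 + 0.2475 + 0.0475 + 0.16)/20) = 0.357.
- Case 2, 20 per cell: 1.96 × √((0.21 + 0.2475 + 0.1275 + 0.1275)/20) = 0.370.
- 28 rural and 12 urban per arm: 0.407 and 0.408.
- 12 rural and 28 urban per arm: 0.372 and 0.399.

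For T2 knowledge adjusted for T0, the half-width in SD is 1.96 × √(4/n) × √(1−r²), where r is the T0–T2 correlation:

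| Patients per cell | r = 0 | r = 0.5 | r = 0.7 |
|---|---|---|---|
| 20 | 0.88 | 0.76 | 0.63 |
| 12 (60% of 20) | 1.13 | 0.98 | 0.81 |

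For race, 0.09 × 40 = 3.6 Black patients per arm, too few for a useful interval.

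**The case against.** The strongest reply is that this is one loose phrase. It is hedged, no formal effectiveness hypothesis is tested, Section 4.1 glosses equity as reach, and the Table 2 row profiles responders, which suits that gloss. This is why rewording alone is a sufficient repair. It does not remove the mismatch: the phrase stands in a stated objective in two places, and exploratory status excuses imprecision, not estimating a different quantity.

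A second point is that the Equity row concerns patients who seek referral, which the tool itself prompts, so subtracting usual care means little there. That is fair for seeking. But Section 3 names referrals among the effectiveness outcomes, and Table 2 measures referrals received in each arm.

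Third, the illustration depends on assumed rates, and these limits stand. Case 1 needs a fourfold usual-care difference. Its effects are equal in percentage points but not as risk ratios (30/5 = 6.0 rural, 45/20 = 2.25 urban). In case 2 usual care does not differ, so the mPal-only gap of 15 points is the true difference in effect, estimated more precisely (half-width 0.296 against 0.370). The 80% counts any difference, even one patient; a two-sided Fisher test at 0.05 on the mPal-only data would be significant in about 10% of repetitions. The both-arm contrast also shows some nonzero gap in about 89% of case 1 repetitions, though with no preferred direction. None of this lets a reader of mPal-only data tell case 1 from case 2.

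Finally, 40 per arm cannot establish similar effects even with controls. That is correct.

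**Conclusion.** The concern holds. As written, the plan cannot answer the question in Objective 2, because the mPal-only contrast mixes any difference in effect with any subgroup difference under usual care. That conclusion follows from the design and does not depend on assumed numbers. How misleading the tables would be does: the 80% rests on the assumed 30% and 45% referral rates with 20 patients per group, and the error disappears if usual-care outcomes do not vary by characteristic. The documents give no figures on that.

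The consequence is limited to an exploratory aim of a feasibility pilot. The primary endpoint is unaffected. The change is still worth making, because it alters what the trial can conclude about equity and costs little.

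**What to change.** Either change is sufficient.

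1. **Add one exploratory both-arm table.** By characteristic, give the mPal minus usual-care difference in T2 knowledge and in EHR referral received by 3 months, and the between-subgroup difference in effect with its 95% CI.
   - Use the same knowledge score as in the overall comparison in Section 10.4.3.
   - Adjust for the original T0 value in both arms, because the repeat baseline in Section 9.1 applies only to patients who view mPal.
   - Count referral from randomization in both arms.
   - State that the table reflects only the randomized patient-level component (Section 7.1).
   - Show very small subgroups, such as about 4 Black patients per arm, as counts without an interval.
2. **Reword Objective 2** in Sections 1.1 and 3 to reach and response among mPal patients, and draw no conclusion about similar effectiveness.

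In both cases keep the mPal-only tables and interviews, worded as reach and response in line with Section 4.1.

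Option 2 is a wording edit in two places. Option 1 needs a short text addition and one table from data already planned: T0 demographics, T0 and T2 knowledge, and dated EHR referrals available for up to 12 months. Its drawbacks are intervals of about ±36 to 41 points for referral and ±0.63 to 1.13 SD for knowledge, with a risk of over-reading. A window counted from randomization also includes time before mPal is viewed, possibly more than 30 days after baseline. A control arm does not remove ceiling effects, and the pilot would still not settle the question.
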